# I. Hypotheses and Specific Aims:

Hypothesis: Sodium fluorescein, which has been shown to be useful for intraoperative guidance regarding the resection of adult neurosurgical tumors, can aid the resection of pediatric neurosurgical tumors.

Specific Aims: To study the utility of sodium fluorescein when used in conjunction with a surgical microscope equipped with fluorescent filters in the resection of pediatric central nervous system tumors (i.e. brain tumors and spinal tumors).

# II. Background and Significance:

Several techniques using fluorescent biomarkers have been investigated as means to identify and delineate brain tumors from critical neural and vascular structures, and to facilitate resection of multiple types of adult brain tumors. In certain tumor types, such as adult gliomas, extent of resection is a primary determinant of outcome and is associated with longer life expectancy [1]. Unfortunately, glioma heterogeneity and the diffuse infiltrative nature of the tumors make complete resection difficult. Thus, in glioma as well as other types of nervous system tumors, improving the intraoperative detection of residual tumor while preserving normal tissue is crucial. Consequently, methods that can aid in achieving gross total resection while minimizing the risk of damaging normal adjacent tissue are of clinical significance and direct utility to patients. Currently, multiple surgical adjuncts exist, including intraoperative ultrasound, frameless sterotaxy, and intraoperative MRI.

Recent research in fluorescein-guided microsurgery has emerged as an additional adjunct to these tools. The two most commonly used and researched agents are 5-ALA and sodium fluorescein. 5-ALA is a metabolic precursor protein to the heme biosynthesis pathway that leads to the accumulation of a fluorescent protein, protoporphyrin IX, in gliomas when administered exogenously [2]. In their study, Stummer et al. examined the use of 5-ALA to determine if its use would lead to better tumor visualization, more complete resection, and potentially increased survival. They concluded that in addition to age, residual solid fluorescence and absence of contrast enhancement on post-operative MRI were independent explanatory factors for survival. The authors concluded that 5-ALA-induced tumor fluorescence was useful for guiding tumor resection. 5-ALA however is very expensive and currently not FDA approved for surgical resection of central nervous system tumors.

Sodium fluorescein is an exogenous green fluorescent contrast agent whose use has been mostly limited to ophthalmologic angiography for the diagnosis of malignancies and vascular lesions. Sodium fluorescein was first used in neurosurgery in 1948 and has been found to be safe for use in neurosurgery [3,5,7]. The use of systemically-delivered intra-operative fluorescein has been evaluated in gliomas (low-grade and high-grade), metastatic tumors, and various skull base lesions including schwannoma, meningioma, craniopharyngioma, and pituitary adenoma [6-13]. Koc et al. compared the influence of fluorescence guided resection in gliomas on gross total resection and survival in patients versus those who underwent standard microsurgical resection and found that the extent of fluorescence had a powerful effect on the rate of gross total resection (83% vs. 55%) despite no statistically significant difference in survival between the groups. Okuda et al., found that the use of fluorescein-guided resection may reduce the rate of local recurrence in patients with metastatic lesions, and da Silva et al., introduced the possibility of using fluorescein-guided

[name]: 18-0242 Page 1 Version: 07/03/2019

resection in skull base surgery for various lesions [11,14]. Recent groups have taken the concept of fluorescein-guided resection further by developing a microscope capable of emitting excitatory light and detecting fluorescence from sodium fluorescein in an effort to further maximize resection rates [12].

Significantly, systemically delivered sodium fluorescein has been found to be useful in guiding the resection of adult central nervous system tumors and has been found to be safe and effective as an intraoperative tool. Thus far, there has been a paucity of research exploring the usefulness of sodium fluorescein in the surgical resection of pediatric tumors [15].

Particular advantages may exist in the resection of spinal tumors, for which other operative adjuncts (e.g. neuronavigation) are not available. Spinal cord anatomical and physiological composition is very similar to the composition of the brain. The blood brain barrier is also present in the spinal cord of adults and pediatric patients and is composed of astrocytes. Tumors within the spine cause disruption of the spinal cord blood brain barrier and permit for extravasation of both contrast as well as sodium fluorescein [5]. In the absence of tumors, sodium fluorescein does not non-specifically extravasate into the parenchyma and this has been shown in spinal vascular applications [5,11,16]. Our institution has demonstrated safe administration and use of sodium fluorescein in adult spinal populations and we plan to apply this to our pediatric patient population as well. [17,18] We will utilize a phased method of enrollment and enroll patients with spinal lesions into the second phase of our study. Pediatric patients have a relatively high incidence of spinal tumor and would benefit from the use of sodium fluorescein which may prove to be crucial in the maximal safe resection of these lesions.

# III. Preliminary Studies/Progress Report:

To date, there are no published data using sodium fluorescein for the resection of central nervous system (CNS) tumors in children. Our group has considerable experience with the use of sodium fluorescein in adult tumors [19-20].

The neurosurgeons at Children's Hospital Colorado have extensive experience with pediatric brain and spine tumor surgery. They perform approximately 100 tumor surgeries each year, making them one of the busiest groups in the country. Their relevant research experience is formidable, having published 25 research articles related to brain and spine tumors in the last two years alone. Two of these papers were specifically about the use of sodium fluorescein in guiding adult brain tumor resections.

#### IV. Research Methods

### A. Outcome Measure(s):

The primary outcome measure will be extent of tumor resection. For all patients, pre-operative imaging and post-operative imaging will be used to analyze the extent of resection of the tumors. In intracranial lesions, the use of volumetric imaging tools will be used to calculate the extent of tumor resection. In spinal lesions, manual measurement will be used to determine the extent of resection.

Secondary outcome measures include the subjective utility of fluorescein per the operating surgeon, as well as positive predictive value, sensitivity and specificity for extent of tumor resection. Additional outcome measure(s) will vary depending on the neurosurgical tumor removed. Intraoperative videos and images will be collected from the surgical case. Images obtained will be correlated to tissue biopsy and will aid in the analysis of fluorescein

[name]: 18-0242 Page 2 Version: 07/03/2019

extravasation in pediatric neurosurgical tumors. All tissue samples collected will be taken for histopathological analysis.

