Given this, we propose a 3:1 ratio of historical controls to fluorescein treated patients to match tumor location and histology. 150 historical controls will be pulled from the last ten years of Children's Hospital patients and matched to the 50 fluorescein treated cases on lesion location and pathology. This 3:1 ratio will strengthen our ability to objectively assess for adverse events related to sodium fluorescein as well as our extent of tumor resection analysis. Importantly, historical controls undergo stereotactic-guided tumor resection in a similar fashion to patients undergoing fluorescein administrations as outlined in our protocol.

All patients who undergo sodium fluorescein-aided resection will also have neuropathological analysis. We will analyze correlation of fluorescein staining to histopathology. Tissue obtained during the time of surgery will be used to correlate fluorescein staining to histopathological diagnosis. This data will be used to calculate sensitivity and specificity of fluorescein staining for tumors. Pre- and post-operative imaging will be used to assess the degree of the extent of resection in intraparenchymal tumors. Data collected from post-operative follow-up will be used to assess for potential complications/adverse reactions associated with sodium fluorescein administration.

For data analysis, extent of tumor resection will be compared as a continuous value across groups using a parametric ANOVA. Further calculations, such as sensitivity, specificity and positive predictive value will be calculated by contingency tables. Additionally, since group membership is not random we will run an adjusted analysis predicting the likelihood of tumor resection as a continuous outcome adjusting for demographic and co-morbidity factors. Significance will be assigned at p < 0.05.

Furthermore, adverse reactions and population/demographic data will be characterized using relative risk and odds ratios. Overall survival and progression free survival analysis will be characterized using Kaplan-Meier curves and compared across groups using a log rank test.

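### Spinal extent of resection has an undefined manual measure but falls under the same single ANOVA as the volumetric intracranial results, so the pooled difference may lack one clear meaning

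*Combined protocol and SAP*

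**What the plan says.** Section IV.A (Outcome Measures) names one primary outcome for every patient: "The primary outcome measure will be extent of tumor resection". It then assigns two methods. For the brain: "In intracranial lesions, the use of volumetric imaging tools will be used to calculate the extent of tumor resection". For the spine: "In spinal lesions, manual measurement will be used to determine the extent of resection". Neither the dimension measured by hand nor the formula that turns it into an extent of resection is stated.

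Section IV.F (Data Analysis Plan) gives one primary analysis: "extent of tumor resection will be compared as a continuous value across groups using a parametric ANOVA". It contains no stratification by site, no separate spinal analysis and no conversion between methods. The adjusted model is described as a "continuous outcome adjusting for demographic and co-morbidity factors"; neither site nor measurement method is named. The power calculation in the same section uses one mean difference (16 points) and one SD (25) for all patients.

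Two other statements in IV.F bear on the point. Controls are "matched to the 50 fluorescein treated cases on lesion location and pathology", at three controls per case. And one sentence reads: "Pre- and post-operative imaging will be used to assess the degree of the extent of resection in intraparenchymal tumors". Taken literally this is narrower than IV.A, which applies pre- and post-operative imaging to all patients.

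**The concern.** A percent reduction depends on what is being reduced. A residual with half the original diameter is 50% resected by diameter, 75% by area and 87.5% by volume, assuming uniform shrinkage. If the spinal measure is a diameter or an area, one ANOVA averages percentages that do not mean the same thing. The pooled treatment difference is then a blend whose value depends on the spinal share and on the unstated definition. A gap in level between the two kinds of percentage also adds to the within-group spread.

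At stake are the interpretation and precision of the primary result. A further risk lies in the controls. Spinal controls come from up to ten years of past cases, and without a written definition nothing ensures that their scans are measured in the same way as those of the treated patients.

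**Working it through.** **Inputs.** Means 93.1% and 77.1%, SD 25, alpha 0.05 (IV.F). Planned size 50 treated and 150 controls (IV.C, IV.F). Spinal share w = 0.20 from IV.C (10 of 50, one of five tumour types with ten patients each) or w = 0.10 from IV.F (about one in ten). The documents give no spinal mean, SD or effect, so those are assumed below.

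**Step 1: the plan's own figure.** A two-group one-way ANOVA is a two-sided t-test. With effect size 16/25 = 0.64 and equal groups, the noncentral t gives totals of 64, 80 and 106 for 70%, 80% and 90% power. Table 3 reproduces exactly. At the planned 50 v 150 the power is 97.4%.

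**Step 2: the plan's means on other scales.** Assume that the planning means are volumetric and treat each as one uniformly shrunken tumour. The residual diameter fraction is d = (1 − volume resected)^(1/3).

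- Control: d = 0.229^(1/3) = 0.612. Treated: d = 0.069^(1/3) = 0.410.

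| Scale | Control | Treated | Gain (points) |
|---|---|---|---|
| Volume, 1 − d³ | 77.1 | 93.1 | 16.0 |
| Area, 1 − d² | 62.6 | 83.2 | 20.6 |
| Diameter, 1 − d | 38.8 | 59.0 | 20.2 |

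**Step 3: pooled difference.** With equal spinal shares in both groups, pooled difference = (1 − w) × 16 + w × spinal gain.

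- w = 0.20: 12.8 + 0.2 × 20.2 = 16.8 (diameter); 12.8 + 0.2 × 20.6 = 16.9 (area). The shift is 5% to 6%.
- w = 0.10: 14.4 + 2.02 = 16.4 (diameter); 14.4 + 2.06 = 16.5 (area). The shift is about 3%.

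**Step 4: direction.** From a residual diameter of 0.4 to 0.2, the gain is 20 points by diameter and 5.6 by volume. From 0.8 to 0.6, it is 20 by diameter and 29.6 by volume. The spine can therefore count for more or for less than on the volume scale, depending on residual size.

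**Step 5: spread.** Within a group, variance = (1 − w) × 25² + w × (spinal SD)² + w(1 − w) × (spinal level offset)². The two group variances are then pooled with weights 49 and 149 over 198.

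- At the step 2 values with spinal SD 25, the offsets are −38.3 (control) and −34.1 (treated) for diameter, and −14.5 and −9.9 for area. With w = 0.20 the pooled SD is 29.1 (diameter) or 25.6 (area). Power at 50 v 150, using the step 3 differences, is 94% or 98%.
- A wider assumed range takes a control-group offset of 0 to −30, spinal SD 25 to 35 and a spinal effect of 16 down to 0 points on its own scale. The pooled SD then runs from 25.0 to 30.6. Power falls from 97.4% to as low as 72.2% (w = 0.20) or 87.6% (w = 0.10). Part of that loss comes from the assumed smaller spinal effect, not from the scale.

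**Step 6: analysing the sites apart.** With the plan's 16 points and SD 25 at 3:1: intracranial only, 40 v 120, 93.6% (45 v 135 if the spine is one tenth, 95.9%); spinal only, 10 v 30, 40.1%.

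**The case against.** The strongest reply is that the plan states two methods, not two scales. Manual measurement could be a volume derived by hand from three diameters, and the mismatch would then be small. Nor does IV.F say outright that brain and spine enter the ANOVA together; its imaging sentence even mentions only intraparenchymal tumours. Both observations are correct. Different scales and pooling are inferences. What is certain is that part of the primary outcome has no defined measure, and that the only analysis described makes no provision for site.

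A reader might go further and infer that the treatment comparison is biased, because a level gap between scales can be larger than the 16-point planning effect. The documents do not support that. Matching on location gives both groups the same spinal share, so a level gap is common to both if they are measured alike.

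A reader might also infer that spinal cases are over-weighted, with larger spread, and that the pooled effect is greatly inflated. Step 4 shows that the direction depends on residual size, and the shift is small at the plan's own means. Nor can one conclude that the result is not comparable with the planning figures: the documents do not say how the cited adult study measured resection.

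**Conclusion.** The point stands as a weakness in the definition and analysis of the primary outcome. The spinal measure is undefined, and nothing in IV.F harmonises it with volumetry or separates the two sites. If it is a diameter or an area, the pooled difference has no single meaning and its SD may rise. This is harm to interpretation and precision, not a demonstrated bias, and that conclusion rests on matching holding and on cases and controls being measured alike.

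The size is modest and uncertain: a shift of about 3% to 6% in the pooled difference, given a spinal share of 10% to 20%, volumetric planning means and uniform shrinkage. If the manual measure already yields a volume, little remains beyond writing it down. Table 3 is unaffected.

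**What to change.** 1. In IV.A, define spinal extent of resection as percent volume reduction, (pre-operative volume − residual volume) / pre-operative volume. Obtain volume by segmentation or by the ellipsoid formula from three orthogonal manual diameters. State that the same rule applies to treated cases and historical controls. Settle this before the second-phase spinal cases are measured.
2. In IV.F, add site (intracranial or spinal) as a factor in the ANOVA and show the results by site as well. The factor absorbs a difference in level; the results by site show whether the effects differ.
3. If another manual measure is kept, make the intracranial volumetric comparison primary and report the spine separately as descriptive. The intracranial analysis keeps about 94% power under the plan's assumptions. The cost is that the spinal comparison, at about 40%, cannot support a conclusion by itself.
4. Reconcile the intraparenchymal sentence in IV.F with the all-patients statement in IV.A, and the one-tenth spinal share in IV.F with the 10 of 50 in IV.C.

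The cost is protocol wording and a few more measurements per spinal scan on images already taken as standard care. Ellipsoid volumes are only approximate for irregular spinal lesions.

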# B. Description of Population to be Enrolled:

Potential study participants include patients between 31 days and 21 years old, who are being seen at Children's Hospital Colorado for a central nervous system tumor (brain and spine tumor) and are undergoing neurosurgical resection. Enrollment will include 2 subsequent phases with the following tumor types in each phase:

# First Phase of Study:

- High Grade Glioma
- Pilocytic Astrocytoma

# Second Phase of Study:

- Medulloblastoma
- Ependymoma
- Contrast Enhancing Spinal Tumors

#### Inclusion Criteria:

- Age 31 days through 21 years on date of surgery
- Undergoing resection of a central nervous system tumor at Children's Hospital Colorado
- Parent/legal guardian (or adult subject) willing and able to complete the informed consent process

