#### **Exclusion Criteria:**

- Tumor in functionally eloquent cortex that precludes maximal surgical resection
- Severe renal dysfunction
- Preoperative serum creatinine level > than normal range and GFR < 30.

- Severe liver dysfunction
- History of asthma or pulmonary spasm
- Known allergy to sodium fluorescein or any other contrast dye
- Previous administration of sodium fluorescein within the last 72 hours
- Pregnant or nursing mother
- Other unspecified reasons that, in the opinion of the investigator, make the subject unsuitable for enrollment.
- Tumors with primary differential diagnosis not included in the inclusion groups

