[name]: 18-0242 Page 6 Version: 07/03/2019

physical, neurologic exam data, and may also include laboratory findings and post-operative imaging studies. These will all be documented clinically and recorded via chart review for the study. Patients will be followed for the study through Month 2 (or 8 weeks) post-surgery.

Furthermore, any adverse events occurring after surgery will be collected until 7 (for non-serious AEs) or 30 days (for SAEs) after the last day of study intervention (administration of fluorescein). All adverse events will be followed for outcome information until resolution or through Month 6 post-surgery.

For example, if a patient has no adverse events following surgery, they will only be followed through end of study period which is 2 months post-surgery. If the patient had adverse events within the first 30 days, those adverse events will be followed through resolution or 6 months post procedure, whichever comes first.

Re-Enrollment: Patients who have previously been enrolled in this study and received prior administration of fluorescein sodium as a part of this study for guided tumor resection are eligible for re-enrollment into the study, should further surgical resection be clinically indicated. Patients will receive the same dosage as outlined in the protocol of 3mg/kg. Clearance of 500mg of fluorescein sodium is 24-72 hours after administration of a single dose [16]. Patients re-enrolled into the study will be eligible after 3 days given the clearance time necessary for fluorescein sodium. Patients will be enrolled with the same study number. Patients will be reconsented at time of re-enrollment.

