## f. Adverse Event Reporting

Adverse Event Reporting will be performed in accordance with the study protocol, any contractual agreement, and all IRB requirements.

21 CFR 312.64(b) requires that the Site Principal Investigator records non-serious adverse events and reports them to the Sponsor according to the timetable for reporting specified below.

**Disease-Related Events (DREs):** The following disease-related events (DREs) are expected and common with brain tumor surgery, and will not be reported per the standard process for adverse event reporting: bleeding in the brain, injury or swelling to the brain, infection in the brain or at wound site, meningitis, seizures, hydrocephalus, cerebral spinal fluid leakage, the need for

[name]: 18-0242 Page 11 Version: 07/03/2019

additional surgery, tearing of the eyes, damage to the eye, blood clots, stroke, dizzy spells, recurrence or tumor growth, postoperative pain and allergic reactions to anesthesia.

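### First and repeat resections are both eligible, but controls are matched only on lesion location and pathology, so an unequal mix between arms could bias the extent-of-resection comparison

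*Combined protocol and SAP*

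**What the plan says.** Section IV.B (Inclusion Criteria) admits a patient who is "Undergoing resection of a central nervous system tumor at Children's Hospital Colorado". None of the Exclusion Criteria concerns earlier tumour surgery. The only one that looks back at an earlier administration is "Previous administration of sodium fluorescein within the last 72 hours".

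The Re-Enrollment paragraph of section IV.C says that patients already treated in the study "are eligible for re-enrollment into the study, should further surgical resection be clinically indicated". It adds "Patients will be enrolled with the same study number", but does not say whether the second operation counts toward the ten per pathology, receives its own controls or enters the primary analysis.

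Section IV.F sets up the comparison: "150 historical controls will be pulled from the last ten years of Children's Hospital patients", and these are "matched to the 50 fluorescein treated cases on lesion location and pathology". The primary outcome in section IV.A, extent of resection from pre- and post-operative imaging, is compared by a parametric ANOVA. Because assignment is not random, an adjusted analysis is added, with demographics and comorbidities as the only named covariates. First versus repeat resection is not a matching factor, stratum, covariate or exclusion anywhere in the document.

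**The concern.** Extent of resection is measured against the tumour present before that operation. In a repeat operation the starting point is residual or recurrent tumour in a bed already operated on, which may be a different surgical task from a first resection. The two kinds of operation may therefore have different expected values of the primary outcome without any effect of fluorescein.

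The two stated matching factors cannot separate them, because a first and a repeat operation on the same tumour have the same location and the same pathology. Prior resection is neither a demographic factor nor, on an ordinary reading, a comorbidity, and the plan defines neither term. In a non-randomised comparison, matching and adjustment are the only protection against confounding, and neither covers this factor. If one arm holds more repeats than the other, the imbalance passes straight into the estimated difference.

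**Working it through.** **Inputs from the plan (sections IV.C and IV.F).** Difference 16 points (93.1 − 77.1), SD 25, alpha 0.05, 50 treated and 150 controls.

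**Assumed inputs (the documents give none).** D is the number of points by which repeat operations fall short of first operations, varied from 5 to 20. s is the difference between arms in the share of repeats, varied from 10 to 30 percentage points. The SD is held at 25.

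**1. The plan's own figure.** A two-group one-way ANOVA with equal groups has effect size f = 16/(2 × 25) = 0.32. This gives totals of 64, 80 and 106 for 70%, 80% and 90% power, exactly as in Table 3. The normal approximation gives 62, 78 and 104. The table is sound on its stated inputs.

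**2. Precision at the planned size.** SE = 25 × √(1/50 + 1/150) = 4.08 points. Power for 16 points at 50 versus 150 is 97.5%.

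**3. Effect of an unequal mix.** Absolute bias = s × D. For example, 0.20 × 10 = 2 points and 0.20 × 20 = 4 points. The two-sided rejection rate with no true effect is 1 − Φ(1.96 − bias/SE) + Φ(−1.96 − bias/SE). If the bias runs against fluorescein, power for a true 16 points is Φ((16 − bias)/SE − 1.96).

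| Combinations (s, D) | Bias | False-positive rate | Power if bias is against fluorescein |
|---|---|---|---|
| 10, 5 | 0.5 | 5.2% | 96.7% |
| 20, 5 or 10, 10 | 1 | 5.7% | 95.7% |
| 20, 10 or 10, 20 | 2 | 7.8% | 92.9% |
| 30, 10 | 3 | 11.4% | 89.0% |
| 20, 20 | 4 | 16.5% | 83.6% |
| 30, 20 | 6 | 31.2% | 68.8% |

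The noncentral t with 198 degrees of freedom gives 7.8%, 16.4% and 31.0% for biases of 2, 4 and 6 points.

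**4. One child in both arms.** Suppose m children contribute an operation to each arm, with within-child correlation ρ (both assumed). The variance of the difference is then 625 × (1/50 + 1/150) − 2mρ × 625/(50 × 150). For m = 5 and ρ = 0.3 the true SE is 4.05 and the actual alpha 4.8%. For m = 25 and ρ = 0.7 they are 3.71 and 3.1%. Dependence alone makes the test slightly conservative. If 10 of the 150 controls were such operations and removed 20 points less (both assumed), the shift would be 10/150 × 20 = 1.3 points.

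**5. Cost of restricting to first resections.** If 10%, 20%, 30% or 40% of the 50 treated operations were repeats (assumed), 3:1 matching would leave 45:135, 40:120, 35:105 or 30:90. Power for 16 points would be 96%, 94%, 91% or 86%.

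**The case against.** The strongest reply is that no imbalance has been shown. Both arms come from the same hospital, neither is restricted to first operations, and no repeat share is given. The two inputs that drive the bias have no anchor in the documents, and the largest figure needs a 30-point imbalance and a 20-point deficit together. The study is also described as a pilot, and section IV.E already names the lack of a randomised control as a limitation. All of this stands, and it limits the point to a possible bias of unknown size. It does not remove the gap, because the planned matching and adjustment would leave such an imbalance uncorrected.

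A reader might infer more than the documents support:

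- **That the bias favours fluorescein.** It would do so if repeats were over-represented among controls and had lower resection. An excess of repeats in the treated arm, which the re-enrollment rule permits, would work against fluorescein.
- **That treated children's own failed operations will serve as controls.** No rule bars this, but section IV.C counts treated patients and historical controls separately, and nothing prefers a child's own earlier operation. The re-enrollment rule is not evidence for it, because the earlier operation there used fluorescein. By the working above, the effect is small. Operations followed by recurrence also belong in a historical pool at their natural frequency. Removing all of those from later-treated children selects controls on a future event and could raise the control mean.
- **That the plan declares repeat resection frequent.** Section IV.G.1.f calls certain events "expected and common with brain tumor surgery", and its list includes further surgery and recurrence. That list only exempts post-operative events from standard reporting. It does not say how many children enter with an operated tumour.
- **That staining accuracy is distorted in an operated bed.** Section IV.C says the dye collects where the blood-brain barrier is impaired. No text says that an operated bed stains without tumour.

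**Conclusion.** The omission is real. First and repeat resections are both eligible, repeats are expressly allowed in the treated arm, and the plan does nothing to balance them in the primary comparison. The consequence is conditional. With an assumed 20-point difference in repeat share and a 10- to 20-point deficit, the bias is 2 to 4 points, or one eighth to one quarter of the planned 16. The false-positive rate is then about 8% to 16% if there is no true effect. These figures show what could happen, not what is likely, and the direction is unknown. Overlap of children between arms is a minor matter. The point is worth settling before controls are chosen, because a matching or covariate rule written after outcomes are known invites selection.

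**What to change.** In section IV.F, state that every treated and control operation is coded as a first or repeat resection of that tumour. For treated children the source is the medical history already collected under Table 1; for controls it is the hospital chart. Add the code to location and pathology as a third matching factor. Where three matched controls cannot be found, include it as a covariate in the adjusted analysis. Report a sensitivity analysis of extent of resection limited to first resections.

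As a minor addition, state that no child contributes operations to both arms, or show by sensitivity analysis that dropping such controls leaves the result unchanged. The second option avoids selecting all controls on a later event.

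The cost is one chart variable and a few sentences. The downside is that some repeat cases may get fewer than three controls. The first-resection analysis would keep about 86% power for the planned difference even if 40% of treated operations were set aside.
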